# **STUDY SYNOPSIS**

MDACC Protocol Number	2018-1059
Protocol Version	November 18, 2022
(Date)	110.10111101110111101111111111111111111
Trial	Single Institution Trial (MDACC)/USA
Center/Country	
Planned Trial	January 2020/January 2025
Period (First Subject In/Last	
Subject Out)	
Trial Registry	February 12, 2020 clinicaltrials.gov
Study Population	Patients with advanced solid tumors with DNA Damage Response aberrations
Study Design	This is an open label, single center Phase I/II dose escalation and expansion study that will evaluate the safety and clinical benefit of the following combinations:
	IV ATR inhibitor (M6620) in combination with avelumab.
	Note: Additional arms involving agents, such as an oral ATR inhibitor, DNA-PK inhibitor, a PARP inhibitor, an ATM inhibitor, and other agents will be added following a substantial amendment to the current protocol.
Objectives	Primary Objectives
	
 
To determine the safety and tolerability of the combination of M6620 and avelumab in patients with DDR deficient advanced solid tumors.
 

	
 
To establish the maximum tolerated dose (MTD) and recommended phase 2 dose (RP2D) of the combination of M6620 and avelumab in patients with DDR deficient advanced solid tumors.
 

	Secondary Objectives
	
 
To determine the clinical benefit of the combination of M6620 and avelumab, as defined by clinical benefit rate (CBR) - complete response [CR] + partial response [PR] + stable disease [SD] > 6 months (CR + PR + SD > 6 months).
 

	
 
To assess clinical benefit of the combination as defined by objective response rate (ORR = CR + PR), overall survival (OS), and progression free survival (PFS).
 

	Exploratory Objectives
	To evaluate clinical benefit of the combination of M6620 and avelumab based on specific DDR aberrations.

- 2. To evaluate clinical benefit of the combination of M6620 and avelumab based on DDR gene expression signatures.
- 3. To evaluate the impact of treatment on PD-L1 expression and immune cell populations.
- 4. To assess potential mechanisms of resistance by comparing preand on-treatment biopsies in responders and non-responders.
- To evaluate the pharmacokinetic (PK) and pharmacodynamic (PD) profile of M6620 in combination with avelumab in patients with DDR deficient advanced solid tumors.

### **Endpoints**

### **Primary Endpoints**

- Incidence and severity of adverse events (AEs) and serious adverse events (sAEs) (as graded by NCI CTCAE version 5.0), including significant changes in laboratory parameters, ECGs, and vital signs.
- Incidence of dose-limiting toxicities (DLTs) (see Section 3.3).

### Secondary Endpoints

- 1. Clinical benefit will be assessed radiographically per Response Evaluation Criteria in Solid Tumors (RECIST) version 1.1, and immune-related RECIST (irRECIST). Post-baseline imaging will occur every 2 cycles or 8 weeks (± 7 days) for the first year of treatment. Thereafter, tumor assessments will be performed every 3 cycles or 12 weeks (± 7 days), independent of cycle delays.
- 2. ORR, OS, and PFS by radiographic disease assessments per RECIST v1.1 and irRECIST. Post-baseline imaging will commence after 2 cycles (8 weeks) of therapy.

### **Exploratory Endpoints**

- 1. Correlation between clinical benefit (CBR, ORR, PFS, or OS) and ATM mutations and/or protein loss.
- 2. Assessment of homologous recombination deficiency (HRD) score and replication stress response defect (RSRD) score.
- 3. Immunohistochemistry, immunofluorescence, and flow cytometry analysis of immune cell subsets and markers, including PD-L1.
- 4. Whole exome sequencing, RNA-sequencing, and Reverse Phase Protein Array (RPPA) analysis of pre-, on-treatment, and optional at-progression tumor biopsies.
- 5. PK summary statistics, concentration-time profiles and parameters (e.g. CL, AUC,  $C_{max}$ ,  $T_{max}$ , half-life if estimable).

Study Considerations	
 
Actionable variant(s) in the following DDR genes, based on next generation sequencing (NGS), will be considered in this trial: ARID1A, ATM, ATR, ATRX, BAP1, BARD1, BRCA1/2, BRIP1, CDK12, CHEK2, FANCA, FANCC, FANCD2, FANCE, FANCF, FANCM, MRE11A, MSH2, NBN (NBS1), PALB2, RAD51, RAD51C, RAD51D, SMARCB1, and VHL. Other appropriate aberrations may be considered for patient selection at the discretion of the PI depending on emerging data.
 
CLIA-approved immunohistochemistry analysis of ATM protein loss may also be considered.
 
Interim analysis of toxicity will be performed in cohorts of 10 patients.
 
Interim analysis for futility will be performed in cohorts of 10 patients.
 

Planned Sample	3-6 patients for dose escalation.
Size	30 patients for dose expansion.
	The accrual may be up to 36 patients

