- 16. M6620 may be administered to patients in the dose escalation phase at 1 of 3 doses: 240 mg/m² (dose level 1), 480 mg/m² (dose level 2), or 120 mg/m² (dose level -1) IV weekly, starting on Cycle 1 Day 1 (Days 1, 8, 15, and 22 of every cycle). M6620 will be administered to patients in the dose expansion phase of at the recommended phase 2 dose (RP2D) established in the dose escalation phase.
- 17. When M6620 and Avelumab are to be administered on the same day (e.g. C1D1, C1D15), avelumab will be infused first, with an interval of at least 1 hour before infusion of M6620.
- 18. CT, MRI, or PET-CT scans will be performed at screening, and then every 2 cycles or 8 weeks (± 7 days) for the first year of treatment. Thereafter, tumor assessments will be performed every 3 cycles or 12 weeks (± 7 days) independent of cycle delays. Confirmatory scans will also be obtained ≥ 4 weeks following initial documentation of objective response (OR) or progression of disease (PD). The type of scan obtained is at the discretion of the investigator as appropriate for the disease. However, the same method should be used for the duration of the study. Baseline brain CT or MRI scan is required for all high risk patients (such as breast, melanoma and other cancer types as determined by the PI/sub I) at baseline (screening). Patients with stable brain metastases present at baseline (screening) will have brain CT or MRI scans performed at each tumor assessment. If bone metastases are present at baseline (screening), then repeat bone imaging is required every 8 weeks for the first 52 weeks of study treatment and every 24 weeks thereafter. Bone imaging is required at the time of confirmation of CR for patients who have bone metastases.
- 19. Relevant tumor markers (e.g., CA125, PSA, and CEA) will be assessed at screening, and on Day 1 of every cycle (± 7 days) this will include blood draws at EOT and Long Term Follow-up.
- 20. One tumor biopsy is mandatory (C1D15), although not mandatory all other tumor biopsies will be strongly encouraged. A core tissue biopsy may be required at baseline if no leftover tissue is available for screening, tissue is older than 1 year, or there is not enough tissue for testing. Tumor biopsies may be performed at baseline (pre-treatment), Cycle 1 Day 15, and at the time of progression/EOT (where feasible).

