# 3.4 Maximum Tolerated Dose (MTD) Definition

In the dose escalation phase for the combination of M6620 and avelumab, patients will be assigned sequentially in groups of up to 6 patients at each dose level. Three to 6 patients will initially be enrolled at each dose level for DLT observation. A total of 6 patients will be enrolled at each dose level in the event that a DLT is observed in 1 of the first 3 patients and/or additional safety data are needed.

The MTD is defined as the highest dose level with less than 2 patients with DLT out of at least 6 patients at the dose level. Management and dose modifications associated with adverse events are outlined in subsequent protocol sections.

The DLT assessment window is 28 days (1 cycle). In the absence of DLTs, patients may continue consecutive treatment. For patients who experience a DLT, they may continue treatment with modifications if the toxicity resolves and at the discretion of the treating physician and the Pl. In the absence of clinical deterioration and if the investigator believes that the patient continues to receive benefit from the treatment, patients may continue to receive study drug(s) after the first indication of progressive disease until a confirmatory scan is obtained.

To understand and safeguard against potential cumulative toxicities the study team will continue to monitor the occurrence of study drug related SAEs and AEs throughout the treatment period and during potential treatment extensions to allow for dose correction in the event of cumulative immune-mediated toxicities.

[figure not shown]
Delayed onset of significant toxicities will be evaluated on a case-by-case basis at the discretion of the PI in consultation with the Safety Monitoring Committee (SMC). At minimum, a review and discussion of potential delayed onset of significant toxicity will take place at review prior to a dose escalation decision.

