# 9.3 Sample Size Determination

There will be 3-6 patients enrolled per dose level in the dose escalation phase of the combination of M6620 and avelumab.

Each dose expansion arm may have up to 30 patients each. A 3-stage design with 10 patients in each stage will be utilized. We will stop after the 1st stage if we see 0 successes in 10 evaluable patients on RP2D, after the 2nd stage if we see < 2 successes in 20 evaluable patients, and we will declare the treatment worthy of further study if we see > 3 successes in 30 evaluable patients. If we set p0 (highest success rate for unacceptable treatment) = 5% and p1 (lowest success rate for acceptable treatment) = 20%, this design has alpha = 5%, 80% power and probability of early termination under p0 of 60% after 1st stage and 79% after either 1st or 2nd stage.

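### The synopsis plans 3-6 patients for the whole of dose escalation, but Sections 3.4 and 9.3 plan 3-6 per dose level; its total of 36 fits the body's rules only with pooling that no section states

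*Combined protocol and SAP*

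**What the plan says.** The Study Synopsis, under Planned Sample Size, gives "3-6 patients for dose escalation" and 30 for expansion, and adds "The accrual may be up to 36 patients".

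The body counts by dose level. Section 9.3: "There will be 3-6 patients enrolled per dose level in the dose escalation phase". Section 3.4: "Three to 6 patients will initially be enrolled at each dose level for DLT observation", with groups of up to six at each level. Footnote 16 of the Study Calendar says "M6620 may be administered to patients in the dose escalation phase at 1 of 3 doses"; Section 3.2 and Table 1 of Section 3.2.1 list the same three levels (-1, 1 and 2), starting at level 1.

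Two statements bear on how escalation ends. Section 3.4 defines the MTD as the "highest dose level with less than 2 patients with DLT out of at least 6 patients at the dose level", and Section 3.5 repeats this definition. Section 3.5 also says that once a third of the patients at a level have DLTs, the level below is to be taken as the MTD. It does not require six patients to have been treated there.

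Expansion may take up to 30 (Sections 3.2 and 9.3). The first futility look in Section 9.3 is at "0 successes in 10 evaluable patients on RP2D". Footnote 16 refers to a "recommended phase 2 dose (RP2D) established in the dose escalation phase". No section says whether escalation patients treated at that dose are among the 30.

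**The concern.** The same document gives two sizes for escalation, and the accrual total is built on the smaller one. Finding the MTD and RP2D is a primary objective, yet six patients in all cannot meet an MTD definition that needs at least six at one level plus experience at another.

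A reader cannot tell how many patients escalation, or the trial, may accrue. Nor can a reader tell which patients form the first ten on the RP2D, the denominator of the first futility look. Intrapatient dose escalation adds to this: Section 3.2.1 says how a patient who changes level is counted for safety, but not for response.

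**Working it through.** **Inputs.** Synopsis: escalation 3-6, expansion 30, total 36. Sections 3.4 and 9.3: at most 6 per level. Study Calendar footnote 16, Section 3.2 and Table 1: three levels. Sections 3.4 and 3.5: an MTD needs fewer than 2 DLTs in at least 6 patients; the escalation decision comes after the first 3 at a level. Sections 3.2 and 9.3: expansion maximum 30.

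**The plan's own figure.** 6 + 30 = 36. This reproduces exactly if 3-6 is the total for escalation.

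**Escalation size if the at-least-six definition governs.** Escalation starts at level 1, so any route to an MTD uses at least two levels.
- Smallest, with full cohorts of three: 6 at the MTD + 3 at another level = 9. If a level closes after DLTs in its first two patients, 6 + 2 = 8. Both exceed 6.
- Largest on two levels: 6 + 6 = 12.
- Largest on three levels: 6 + 6 + 6 = 18. The route is level 1 with 0/3; level 2 filled to 6 and failing with 2 or more DLTs; level 1 filled to 6 and failing; level -1 filled to 6. Refilling level 1 after level 2 fails is inferred from the definition, not written as a step.

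**Escalation size if the next-lower-level sentence is read alone.** When a level fails, the one below becomes the MTD without further enrolment.
- Smallest, with a full cohort of three: level 1 fails in its first 3, total 3.
- Largest: 6 at level 1 + 6 at level 2 = 12.

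The range is then 3 to 12, so an upper limit of 6 is wrong here too.

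**Accrual ceiling.** The pooled column assumes that the RP2D equals the MTD and that six escalation patients there are response-evaluable and count toward the 30.

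| Escalation rule | Expansion separate | Six RP2D patients counted in the 30 |
|---|---|---|
| At-least-six definition, three levels used | 18 + 30 = 48 | 18 - 6 + 30 = 42 |
| At-least-six definition, two levels used | 12 + 30 = 42 | 12 - 6 + 30 = 36 |
| Next-lower-level sentence read alone | 12 + 30 = 42 | 12 - 6 + 30 = 36 |

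Against the stated 36, the differences are 48 - 36 = 12, 42 - 36 = 6, and 0. All entries exclude replacement of patients not evaluable for DLT (Sections 3.3 and 9.1.2) and any intermediate dose level (note to Table 1), neither of which is capped.

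**Check on the 30.** An exact binomial calculation for the three-stage rule (stop at 0/10, stop below 2/20, declare worthy above 3/30) gives alpha 0.049 at 5% and power 0.805 at 20%. Under 5%, early termination is 0.599 after stage 1 and 0.787 by stage 2. These match the stated 5%, 80%, 60% and 79%, so the expansion size is not in question.

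**The case against.** The strongest defence is that 36 may be right. Section 9.3 counts evaluable patients on the RP2D, which does not exclude escalation patients. With pooling, 36 is the ceiling if at most two levels are used, or if the next-lower-level sentence in Section 3.5 governs. This stands as a possible reading. But no section states the pooling, and on that reading escalation can still hold 12 patients, so the 3-6 line fails.

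A second defence is that 3-6 is shorthand for per level. The total of 36 fits that only with the same unstated pooling; without it, 36 is 6 + 30 with escalation counted once.

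Third, the 18-patient route is rare. In cohorts of three, its probability is the product of five terms: 0/3 at level 1; 1/3 at level 2; at least one DLT in the next 3 there; at least two DLTs in the second 3 at level 1; and at most one in the first 3 at level -1. With assumed DLT rates of 30%, 50% and 15% at levels 1, 2 and -1, this is 0.343 × 0.375 × 0.875 × 0.216 × 0.939 = 2.3%. With 10%, 25% and 5% it is 0.729 × 0.422 × 0.578 × 0.028 × 0.993 = 0.5%. This is fair: a ceiling must cover the route, but 48 is not a forecast.

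Two stronger inferences are tempting. A reader might infer that the ceiling simply is 48. The documents do not settle that, because it needs both the at-least-six definition to govern and a separate expansion. A reader might also infer that a limit of 36 would cut the expansion short and cost power. The documents do not call 36 a hard cap, and Section 3.1 allows the number in a basket to be increased.

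**Conclusion.** The synopsis is wrong as written. Its 3-6 for all of escalation contradicts Sections 3.4 and 9.3 and is below what the written rules allow: up to 18 DLT-evaluable patients on one reading of how the MTD is reached, up to 12 on the other. Whether 36 is also wrong depends on two matters the plan leaves open: which MTD statement in Section 3.5 applies, and whether RP2D escalation patients count in the 30. The total is 48, 42 or 36 accordingly, and 36 needs pooling that no section states.

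The bounds rest on the text alone, because Figure 4 (the escalation rules) is not shown in the version reviewed. Actual accrual can be lower, since expansion can stop early and escalation can end without an MTD. No loss of power is claimed.

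**What to change.** 1. In the synopsis, change the escalation line to 3-6 patients per dose level.
2. Reconcile the sentence in Section 3.5 on the next lower level with the at-least-six definition in Sections 3.4 and 3.5. Which rule should apply is for the trial team to decide.
3. State in Section 9.3 whether response-evaluable escalation patients treated at the RP2D count toward the 30, and how a patient who changes dose level is counted.
4. Only then restate the synopsis total, adding that replacements and any intermediate level come on top. It is 48 if the at-least-six definition governs and expansion is separate. It is 42 if the definition governs with six patients pooled, or if the next-lower-level sentence governs with a separate expansion. It is 36 if that sentence governs with pooling.

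The cost is a few sentences in the synopsis and Sections 3.5 and 9.3, and a stated ceiling that may rise by 6 to 12. The three-stage rule does not change.

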# STUDY CALENDAR

							Trea	tmeı	nt Pe	riod						Post	-Treatme	nt
Assessments	Screening		Cycle 1						Cycle 2					e 3 an yond	ıd	End of Treatment (EOT)	Follow-	
Day Visit Window in days	≤ 28 days prior to 1 st dosing of study drug	D1 ± 3	D2- 4	D8 ± 2	D15 ± 2	D16- 18	D22 ± 2	D1 ± 2	D8 ± 2	D15 ± 2	D22 ± 2	D1 ± 2	D8 ± 2	D15 ± 2	D22 ± 2	+ 7	Up Day 30, 60, and 90 after last dose	Every 12 weeks ± 14
																	± 7	
Informed Consent 	Х																	
Verify Eligibility	Х	X																
Medical History 	Х																	
Tumor History	Х																	
Serum or urine Beta- hCG 	Х	Х						X				Х				Х	Day 30 and 60 only	
Protocol/Safet	y Evaluation	าร																
Physical Exam and ECOG 	Х	Х			Х			Х		Х		Х		Х		Х	Х	
Vital Signs 	Х	Χ		Х	Х		Х	Χ		Χ		Х		Χ		Х	Х	
Weight 	X	X			X			X		X		X		X		X	X	
Height	X	- `						- `						- ` `			- ' '	
12-lead ECG 	X							Χ										
ECHO/MUGA 	X											Х				Х		

							Trea	tme	nt Pe	riod						Post	-Treatme	nt
Assessments	Assessments Screening				Cycle 1					Cycle 2				e 3 an yond	ıd	End of Treatment (EOT)	Short- term Follow- Up	Long- term Follow- up
Day Visit Window in days	≤ 28 days prior to 1 st dosing of study drug	D1 ± 3	D2- 4	D8 ± 2	D15 ± 2	D16- 18	D22 ± 2	D1 ± 2	D8 ± 2	D15 ± 2	D22 ± 2	D1 ± 2	D8 ± 2	D15 ± 2	D22 ± 2	+ 7	Day 30, 60, and 90 after last dose	Every 12 weeks ± 14
AE/SAE Assessment 	X	X			Х			X		X		Х		X		X	± 7 X	
Concomitant Medications	X	Х			Х			X		X		Х		X		X		
Survival Status 																		Х
Laboratory Ev		,										,	,	1			,	
Hematology 	X	Х			Χ			Χ		X		X		Χ		X	X	X
Chemistry 	Х	Χ			Χ			Χ		Χ		Х		Χ		Х	Х	Х
Thyroid Function 	Х	Х										Х				Х	Х	
Urinalysis 	X	Χ						Χ				Χ				X		
Coagulation Test 	X	Х						Х				Х				Х	X	
Hepatitis B and C (Hepatitis B surface antigen and core antibody; anti-hepatitis C antibody)	X																	

							Trea	tmei	nt Pe	riod						Post	-Treatme	ent
	Screening			C	ycle 1			Cycle 2 Cycle 3 and							nd	End of	Short-	Long-
Assessments													Be	yond		Treatment	term	term
																(EOT)	Follow-	Follow-
			1	1	1	1	1		1		1			1	1		Up	up
Day	≤ 28 days	D1		D8	D15	D16-	D22	D1	D8	D15	D22	D1	D8	D15	D22	_	Day	Every
\/:a:4 \A/:.a.d.a	prior to		4	_	10	18	10	_		+ 0			_	10	10	+ 7	30, 60,	12
Visit Window	1 st dosing	± 3		± 2	± 2		± 2	± 2	± 2	± 2	± 2	± 2	± 2	± 2	± 2		and 90 after	weeks
in days	of study drug	3		_				_	_								last	± 14
	urug																dose	14
																	dosc	
																	± 7	
Study Treatme	nt		•	ı	1	1	1	ı	1		ı		1	,	1		1	1
Avelumab 		Χ			Χ			Х		Χ		Χ		Χ				
M6620 		Χ		Χ	Χ		X	Χ	Χ	Χ	Χ	Χ	X	Χ	X			
Tumor Measur	ement																	
CT, MRI, or	X													week		X		Х
PET-CT 														year,				
												e١		12 we				
														eafter				
														nation				
														follow				
Delevent	X	V						V					nitiai	OR P	υ. Ι	V		V
Relevant Tumor	X	Χ						Х				Х				X		X
Markers 																		
Research Stud	lies (PK/PD)																	
Tumor	X				Х											Х		
biopsy 					^`													
Liquid	Х				Х							Х				Х		
biopsy 																		
PK Blood		Х			Χ							Х						
Samples																		

							Trea	tme	nt Pe	riod						Post	-Treatme	nt
Assessments	Cycle 1						Cycle 2				Cycle 3 and Beyond				End of Treatment (EOT)	Short- term Follow- Up	Long- term Follow- up	
Day Visit Window in days	≤ 28 days prior to 1 st dosing of study	D1 ± 3	D2- 4	D8 ± 2	D15 ± 2	D16- 18	D22 ± 2	D1 ± 2	D8 ± 2	D15 ± 2	D22 ± 2	D1 ± 2	D8 ± 2	D15 ± 2		+ 7	Day 30, 60, and 90 after	Every 12 weeks
	drug																last dose ± 7	± 14
-Avelumab 		Χ			Χ							Х				Х		
-M6620 		Χ	Χ		Х	Х												

#### Footnotes:

- 1. Informed consent must be obtained prior to undergoing any study specific procedure and may occur prior to the 28-day screening period. The use of remote consenting to obtain informed consent from clinical trial participants using paper or electronic consent forms is allowed in this study
- 2. Medical history includes baseline symptoms as well as a detailed history of prior cancer therapies including start and stop dates, disease progression during or after therapy, as well as discontinuations due to intolerability or any other serious illness.
- 3. For female patients of childbearing potential, who do not fit the definition of 'female patients who are not of childbearing potential' in the inclusion criterion, a serum or urine pregnancy test, will be performed on 2 occasions prior to starting study therapy: once at the start of screening (within 28 days of first dose of study treatment), and once at the baseline visit (Cycle 1 Day 1), immediately before administration of investigational agent. Pregnancy tests will also be routinely repeated on Day 1 of every cycle during the active treatment period.
- 4. Physical examination and ECOG will be performed at screening, on Days 1 and 15 of each cycle, and at the End of Treatment (EOT) visit. Physical examinations during the study should be symptom directed.

- 5. Vital signs: temperature, pulse, respiratory rate, blood pressure, body surface area, and body weight will be measured at the start of each treatment cycle (up to 3 day before the start of a new cycle) and on day 15 (± 1 day) of each cycle. Weight will be used to calculate doses per institutional SOP. Height will be obtained from the electronic medical record.
- 6. 12-lead ECG (single) will be performed at screening, and on Cycle 2 Day 1. Thereafter, ECGs will be performed as clinically indicated.
- 7. ECHO/MUGA: will be performed at screening, and on Cycle 3 Day 1. Thereafter, ECHO/MUGA will be performed as clinically indicated.
- 8. AE Assessment: AEs should be documented and recorded at each visit using NCI CTCAE version 5.0. Patients must be followed for AEs for 90 days after the last dose of study drug, or until all drug related toxicities have resolved, whichever is later; or earlier than 30 days should the patient commence another anticancer therapy in the meantime.
- 9. Survival status: investigators will collect survival data for patients after progression of disease unless patient fully withdraws consent to consent to participate in the study. Approximately 1 year after the last dose of treatment, a chart review, patient visit, or telephone call will be conducted. The telephone call should be less than 5 minutes in duration, to obtain information regarding survival status.
- 10. Hematology: complete blood count (CBC), differential, and platelets.
- 11. Chemistry: sodium, potassium, chloride, bicarbonate, blood urea nitrogen (BUN), creatinine, glucose (non-fasting), calcium, phosphate, magnesium, alanine aminotransferase (ALT), aspartate aminotransferase (AST), alkaline phosphatase, bilirubin (total, direct, indirect), lactate dehydrogenase (LDH), total protein, albumin, uric acid, amylase, lipase, creatinine kinase, Adrenocorticotropic hormone (ACTH) and Testosterone (at screening only for CRPC patients), Gamma Glutamyl Transferase (GGT) and C-reactive Protein (CRP). No need to assess on Cycle 1 Day 1 if baseline assessment was performed within 2 days prior to that date. Chemistry labs will be performed on Days 1 and 15 of every cycle.
- 12. Thyroid Function: thyroid-stimulating hormone (TSH), free thyroxine (T4), and total triiodothyronine (T3) will be assessed at screening, Cycle 1 Day 1, and every 2 cycles or 8 weeks thereafter (C3D1, C5D1 etc.,) until disease progression or unacceptable toxicity, and also at the EOT visit.
- 13. Urine analysis will include color, appearance, specific gravity, pH, protein, glucose, ketones, blood, bilirubin, and microscopy including WBC/high power field (HPF), and RBC/HPF, if clinically indicated. Dipstick is acceptable. Urine analysis will be at screening and Day 1 of every cycle. No need to repeat on Cycle 1 Day 1 if baseline assessment was performed within 2 days prior to that date.

- 14. Coagulation test includes prothrombin time (PT), international normalization ratio (INR), and activated partial thromboplastin time (aPTT). Coagulation tests will be performed at screening, and Day 1 of every cycle. No need to repeat on Cycle 1 Day 1 if baseline assessment was performed within 2 days prior to that date.
- 15. Avelumab will be administered to patients at 800 mg, IV every 2 weeks, starting on Cycle 1 Day 1 (Days 1 and 15 of every cycle).
- 16. M6620 may be administered to patients in the dose escalation phase at 1 of 3 doses: 240 mg/m² (dose level 1), 480 mg/m² (dose level 2), or 120 mg/m² (dose level -1) IV weekly, starting on Cycle 1 Day 1 (Days 1, 8, 15, and 22 of every cycle). M6620 will be administered to patients in the dose expansion phase of at the recommended phase 2 dose (RP2D) established in the dose escalation phase.
- 17. When M6620 and Avelumab are to be administered on the same day (e.g. C1D1, C1D15), avelumab will be infused first, with an interval of at least 1 hour before infusion of M6620.
- 18. CT, MRI, or PET-CT scans will be performed at screening, and then every 2 cycles or 8 weeks (± 7 days) for the first year of treatment. Thereafter, tumor assessments will be performed every 3 cycles or 12 weeks (± 7 days) independent of cycle delays. Confirmatory scans will also be obtained ≥ 4 weeks following initial documentation of objective response (OR) or progression of disease (PD). The type of scan obtained is at the discretion of the investigator as appropriate for the disease. However, the same method should be used for the duration of the study. Baseline brain CT or MRI scan is required for all high risk patients (such as breast, melanoma and other cancer types as determined by the PI/sub I) at baseline (screening). Patients with stable brain metastases present at baseline (screening) will have brain CT or MRI scans performed at each tumor assessment. If bone metastases are present at baseline (screening), then repeat bone imaging is required every 8 weeks for the first 52 weeks of study treatment and every 24 weeks thereafter. Bone imaging is required at the time of confirmation of CR for patients who have bone metastases.
- 19. Relevant tumor markers (e.g., CA125, PSA, and CEA) will be assessed at screening, and on Day 1 of every cycle (± 7 days) this will include blood draws at EOT and Long Term Follow-up.
- 20. One tumor biopsy is mandatory (C1D15), although not mandatory all other tumor biopsies will be strongly encouraged. A core tissue biopsy may be required at baseline if no leftover tissue is available for screening, tissue is older than 1 year, or there is not enough tissue for testing. Tumor biopsies may be performed at baseline (pre-treatment), Cycle 1 Day 15, and at the time of progression/EOT (where feasible).

- 21. Blood samples, including for liquid biopsy (cfDNA), will be collected at baseline (pre-treatment), Cycle 1 Day 15, Cycle 3 Day 1, every other cycle thereafter (C5D1, C7D1 etc.,), and at the time of progression/EOT
- 22. Blood draw for Avelumab PK: 3.5 mL whole blood) will be collected (in 3.5 mL SST (VPGOL35) tubes to prepare serum) at: (i) Pre dose and EOI: Cycle 1 Day 1 and cycle 1 Day 15, (ii) Pre dose only: Cycle 3, 6 and (iii) End of treatment sample.
- 23. Blood draw for M6620 PK: (2 mL whole blood in Vacutainer® tubes containing K2EDTA anticoagulant for plasma) will be collected at: pre dose and EOI: Cycle 1, day 1 and Day 15, (ii) Cycle 1, day 2-4 (one sample during this timeframe) and (iii) Cycle 1 day 16-18 (one sample during this timeframe).

